### **Primary Analysis**

To account for the cluster-level-allocation, cluster-level-crossover structure of the trial, the primary analysis will be an intention-to-treat comparison of the primary outcome of MAKE30 between the saline and balanced crystalloid groups using a

Principal Investigators: [name], [name]

Version Date: 6/15/17

Study Title: Isotonic Solutions and Major Adverse Renal Events Trial (SMART)

Institution/Hospital: Vanderbilt University Medical Center

generalized linear mixed-effects model including fixed effects (group assignment, age, gender, race, source of admission, mechanical ventilation, vasopressor receipt, diagnosis of sepsis, and diagnosis of traumatic brain injury) and random effects (intensive care unit).

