## Randomization and Allocation

Each month of the study, each ICU is assigned to either saline or balanced crystalloids. So that each ICU would experience an equal number of months assigned to saline and balanced crystalloids while minimizing monthly imbalances in the hospital's overall use of each crystalloid, we generated two sequences of study group assignment ([1] saline during odd-numbered months and balanced crystalloid during

even-numbered months; [2] balanced crystalloid during odd-numbered months and saline during even-numbered months) and planned for three ICUs to be assigned to one sequence and the remaining two ICUs to the opposite sequence. To facilitate the early administration of the assigned crystalloid in the ED and operating room prior to the patient's physical arrival in the ICU, a single computer-generated, simple randomization was performed in which the three ICUs that admit the majority of patients from the ED (medical ICU, trauma ICU, and surgical ICU) were randomized 'en bloc' to one sequence of crystalloid group assignments and the two ICUs that admit the majority of patients from the operating room (neurological ICU and cardiac ICU) were randomized 'en bloc' to the opposite sequence of crystalloid group assignments (Figures 1-2).

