## Primary Analysis

To account for the cluster-level-allocation, cluster-level-crossover structure of the trial, the primary analysis will be an intention-to-treat comparison of the primary outcome of MAKE30 between the saline and balanced crystalloid groups using a generalized linear mixed-effects model including fixed effects (group assignment, age, gender, race, source of admission, mechanical ventilation, vasopressor receipt, diagnosis of sepsis, and diagnosis of traumatic brain injury) and random effects (intensive care unit)[27,28].

In preparation for SMART, we electronically collected the same set of variables that would be used to analyze SMART from the records of all 11,582 patients admitted to the study ICUs between January 1, 2014 and December 31, 2014. With the data on MAKE30 from the 11,582 patients admitted in the year before the trial, using generalized linear mixed-effects modeling treating the five ICUs as clusters and the 12 months as periods, we calculated the intra-cluster correlation coefficient to be 0.142, the intra-period correlation coefficient to be 0.026, and the intra-cluster intra-period correlation coefficient to be  $<0.001$ .

Using the data from the 11,582 patients admitted in the year before the trial, we performed a series of simulated trials evaluating a variety of trial conditions and potential results including: (1) outcome differences between groups ranging from no difference to a 50% relative risk reduction, (2) heterogeneity of treatment effect by cluster, (3) change in the incidence of the outcome in the control group over the course of the trial, (4) varying levels of intra-cluster correlation, and (5) varying levels of intra-period correlation. In each case the generalized linear mixed-effect model appeared to adequately account for the correlation between participants. Analysis using generalized linear mixed-effects modeling and generalized estimating equations accounting for the same variables produced identical odds ratios and 95% confidence intervals for the difference between the simulated groups in the primary outcome.

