and report not only use of isotonic crystalloid but non-isotonic crystalloid, colloid, and blood product during the trial. Group assignment at the level of the cluster with multiple cluster-level crossovers introduces the possibility for intra-cluster correlation, inter-period correlation, and intra-cluster intra-period correlation which may confound the relationship between group assignment and clinical outcome. In preparatory analyses using data from more than 10,000 patients admitted in the year prior to the trial, we have found the effect of intra-cluster correlation to be minimized by the short periods and frequent crossovers and the effects of intra-period correlation and intra-cluster intra-period correlation to be small. Our primary analysis uses a generalized linear mixed-effects model to account for these aspects of the study structure. In the absence of a washout period, there will be carryover of crystalloid administration from one group assignment into the other, but based on pilot data we anticipate the volume of non-assigned crystalloid received as a result of carryover will be low[14], and we pre-specify secondary analyses to address the effects of carryover. Finally, although MAKE30 is a recommended outcome for clinical trials involving AKI[23,32], use of a composite outcome presents potential challenges. Unlike death and new receipt of renal replacement therapy, whether persistent renal dysfunction on hospital discharge is a patient-centered outcome remains a point of discussion. Persistent renal dysfunction also relies on the availability of serum creatinine measurements at baseline and before hospital discharge – potentially requiring imputation of missing data for one component of the composite primary outcome. Perhaps most importantly, although death, new receipt of renal replacement therapy, and persistent renal dysfunction are weighted equally in the MAKE30 composite outcome, they may not represent equivalent outcomes to patients or providers. To address this we will provide data on the MAKE30 outcome overall and each of its separate components.

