#### Primary analysis

To account for the cluster-level allocation, cluster-level crossover structure of the trial, the primary analysis will be an intention-to-treat comparison of the primary outcome of MAKE30 between the saline and balanced crystalloid groups using a generalized linear mixed-effects model including fixed effects (group assignment, age, sex, race, source of admission, mechanical ventilation, vasopressor receipt, diagnosis of sepsis, and diagnosis of traumatic brain injury) and random effects (ICU) (additional details in Additional file 2) [28, 29].

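### The primary model has no study-month term, although the SAP reports an intra-period correlation of 0.026 and says the model handles it; if months vary independently, the 5% test rejects a true null in about 13–20% of trials

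*Combined protocol and SAP*

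**What the plan says.** The primary model is given three times: in the protocol of 6/15/17 (section 12.0, Primary Analysis), in the SAP (Primary Analysis) and in the published SAP (Primary analysis). The fixed effects are group and eight patient variables. The list closes with "diagnosis of sepsis, and diagnosis of traumatic brain injury) and random effects (intensive care unit") in the SAP, and "diagnosis of sepsis, and diagnosis of traumatic brain injury) and random effects (ICU") in the published version. None of the three lists month or period.

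The SAP's Primary Analysis section also describes a preparatory mixed model on 11,582 patients admitted in 2014, "treating the five ICUs as clusters and the 12 months as periods". It found an intra-cluster correlation of 0.142, "the intra-period correlation coefficient to be 0.026", and an intra-cluster intra-period correlation below 0.001. Simulated trials followed, some with varying intra-period correlation, and the SAP concludes: "In each case the generalized linear mixed-effect model appeared to adequately account for the correlation between participants". No error rate is printed.

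The SAP Discussion names these correlations as possible confounders, calls the period effects small, and adds: "Our primary analysis uses a generalized linear mixed-effects model to account for these aspects of the study structure".

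On allocation (SAP, Randomization and Allocation), "a single computer-generated, simple randomization was performed": the medical, trauma and surgical ICUs follow one alternating sequence, and the neurological and cardiac ICUs follow the opposite one.

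**The concern.** An ICU intercept absorbs stable differences between ICUs. It cannot absorb a good or bad month shared by all ICUs, which is what an intra-period correlation of 0.026 with almost no ICU-by-month component describes.

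Opposed sequences would cancel such effects if each month were balanced between arms. They are not balanced, so part of each month's shock is carried into the treatment contrast while the model's standard error ignores it. If months vary irregularly, the P value and confidence interval of the only confirmatory test are too optimistic, and a positive result could partly reflect which months fell to which fluid. The target difference is only 1.9 percentage points. None of the listed sensitivity analyses varies the handling of month.

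**Working it through.** **1. The plan's own figure.** Power for 15% versus 13.1% with 7,000 per arm: SE = √(0.15×0.85/7000 + 0.131×0.869/7000) = 0.00587; 0.019/0.00587 = 3.236; Φ(3.236 − 1.960) = 0.899. The stated 90% reproduces, as a calculation for individually randomized patients with no ICU or month component.

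**2. Balance within months.** ICU volumes are from Figure 12B of the 5/13/2015 protocol.
- All five ICUs open: (2,300 + 1,693 + 2,126) = 6,119 against (1,212 + 1,892) = 3,104, or 66:34.
- June to September 2015: only the medical ICU enrols, so fluid and month coincide. At those volumes this is about 6% of patients.

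**3. Month variance.** Read as a share of latent logit variance: σ² = 0.026/(1 − 0.142 − 0.026) × π²/3 = 0.103, SD 0.32.

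**4. Effect on the test.** Let w be the information in an ICU-month cell, n×p(1−p). Let d be the cell's arm indicator minus its ICU mean. For an ICU-only model with independent months:

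k² = (true variance)/(model variance) = 1 + σ² × A/D, where D = Σ w d² over cells and A = Σ over months of (Σ over ICUs of w d)².

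The false-positive rate is then 2×[1 − Φ(1.96/k)]. With 14,000 patients, every ICU at 15%, and the start dates in SAP Figure 1:
- Text allocation: D = 444.9, A = 4,204; k² = 1 + 0.1028×4,204/444.9 = 1.97; k = 1.40; rate 16%.
- Grid as printed: A = 1,476; k² = 1.34; k = 1.16; rate 9%.

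**5. Simulation under no treatment effect.** 3,000 trials per setting; Monte Carlo error about 0.4 points at 5% and 0.7 at 17%. The text allocation and the grids as printed were each run with the start dates of SAP Figure 1 and of published Figure 2. As extracted, the two grids disagree, possibly through PDF extraction, and give 84 and 86 unit-months rather than the stated 82, so ranges are shown.

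| Month effects | False-positive rate, ICU-only model |
|---|---|
| Independent, ICU spread 0.142, text allocation | 17–20% |
| Independent, ICU spread 0.142, printed grids | 13–14% |
| Independent, equal ICU rates | 16–17% (text), 9–10% (grids) |
| Serial correlation 0.5 (AR1) | 8–11% |
| AR1 0.8 | 5–9% |
| AR1 0.95 | 5–6% |
| Smooth annual cycle | 5–8% |
| Shocks repeating by calendar month | 23% (text), 7–16% (grids) |
| Independent, effective correlation 0.013 | 9–13% |
| Independent, effective correlation 0.005 | 6–9% |
| 0.026 on the proportion scale, independent | 20–28% |
| 0.026 on the proportion scale, AR1 0.8 | 8–10% |

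With the ICU spread, k was 1.49–1.52 (text) and 1.31–1.34 (grids). The formula in step 4 turns these into 19–20% and 13–14%, in line with the table. Treating ICU as fixed or random made no material difference (17.7% both ways on the same data). A schedule of exactly 82 unit-months (22/18/16/14/12) gave 16–20%. With no month variance the ICU-only model rejects in about 5%, so the excess comes from the omitted term.

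**6. With month in the model.** A random month intercept gave 4.4–5.7% in 24 settings. One smaller run (1,500 trials, AR1 0.8) gave 6.7% against 9.1% for ICU-only; the 3,000-trial runs of that setting gave 5.2% against 6.5–7.7%. Month as a fixed factor gave 3.6–5.8%.

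No patient covariates were simulated.

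**The case against.** The strongest reply is that the large figures need assumptions the plan does not make.
- **Form of the month effect.** The time effects the documents name are seasonality and trends in care. Monthly alternation largely cancels smooth patterns, and the rate is then close to nominal. This stands, and it is why the size is conditional. It does not rule out irregular months: if only a quarter of the month variance is independent, the rate is about 8%.
- **Size of the month effect.** A logit SD of 0.32 puts months (±2 SD) between about 8.5% and 25%, which is wide for an effect the SAP calls small. The scale of 0.026 is not stated, it rests on one year, and the eight patient covariates may absorb part of it. All of this stands as uncertainty, in both directions: the proportion scale gives a worse result.
- **The SAP tested this.** Its simulations did vary intra-period correlation. But the text reports no type I error and does not say whether the simulated model held a period term. Agreement between mixed-model and GEE results on the same variables validates neither if both omit month.
- **Unseen files.** Additional file 2 and the R code are not among the documents here and may contain a month term. If so, the written model is wrong in three places and must be corrected, so action is needed either way.
- **Proportion.** The SAP declares itself final, and a month sensitivity analysis alone would be a lighter remedy. But the SAP already claims that the primary model handles this correlation, so the primary model is where the term belongs.

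**Conclusion.** The concern holds. The written primary model lacks a property that the SAP claims for it. Its false-positive rate is about 13–20% against a nominal 5%, provided that months vary independently, 0.026 is a latent logit share, ICUs differ as the reported 0.142 implies, and covariates absorb none of the month variation. Relaxing these brings the rate down towards 5%; the proportion-scale reading raises it to 20–28%. The omission is certain from the text. Its size is not settled by the documents, so confidence in the magnitude is medium. This should be fixed.

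A minor related point: the SAP (Study Sites and Period) promises each ICU equally many months on each fluid, but 23 alternating months in the medical ICU give 12 saline and 11 balanced.

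**What to change.** - Add study month (23 levels) as a random intercept beside ICU in the primary model, in the protocol, SAP and R code. If the code already has it, correct the text.
- Prespecify month as a fixed factor as a sensitivity analysis. June to September 2015 then adds nothing to the treatment contrast.
- Carry the term into the analyses that repeat the primary one, the interaction models and the secondary-outcome models.
- Report the simulated type I error with and without the term, and state the scale of 0.026.
- Restate power, and give the actual month counts per ICU.

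**Cost.** One model term, from data already held, in a dated amendment made before the final analysis. The standard error rises on average by about 3–10% with random month and 5–13% with fixed month; single extreme ICU patterns can exceed this. Power for 15% versus 13.1% becomes about 82–89%. Little of that is due to the term: with independent months the ICU-only test has 80–87% power and the random-month test 82–88%. At AR1 0.8 the term costs up to about 4 points; if months do not vary, 0.5 points or less.

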## Main Secondary Analysis

Anticipating (1) a wide range in the total volume of crystalloid received by study participants and (2) the potential for greater difference in outcomes between study groups among those patients who receive larger volumes of crystalloid, the main secondary analysis will compare the proportion of patients experiencing MAKE30 in the saline and balanced crystalloid groups, accounting for patients' overall volume of isotonic crystalloid received. For this analysis, we will construct a logistic regression model with MAKE30 as the outcome and independent variables of study group, total isotonic crystalloid received between enrollment and 30 days, and the interaction between the two (as a cross-product term). This will allow us to determine whether any volume of crystalloid receipt exists at which use of balanced crystalloids decreases the risk of MAKE30 compared with saline.

Given that total crystalloid receipt is a variable that emerges after enrollment, we will perform sensitivity analyses (1) using total crystalloid receipt in the 72 hours after enrollment (before incident acute kidney injury or death are likely to have affected isotonic crystalloid administration), (2) replacing the actual total crystalloid receipt with predicted total crystalloid receipt based on a multivariable linear regression model using patient and ICU characteristics available at the time of enrollment derived from crystalloid administration in the study ICUs in the year prior to the trial, and (3) comparing outcomes between study groups among a "modified intention-to-treat" population of patients who received at least 500 mL of any study crystalloid in the 72 hours after enrollment.

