## **8.2 Duration of Treatment**

All patients admitted to study ICUs during the study period will be treated with the study fluid assigned to that ICU until they are physically discharged from the ICU. Enrolled patients who remain in the ICU through a crossover between fluid groups will be treated with the assigned study ICU fluid which will change on the crossover date.

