Although the study focuses on crystalloid use in the ICU, crystalloid administration prior to ICU admission in the emergency department or operating room may introduce contamination and limit separation between study arms. Therefore, between January 1, 2016 and April 30, 2017, the Vanderbilt University Medical Center Emergency Department (ED) is coordinating their crystalloid use with the medical, surgical, and trauma ICUs such that patients admitted to those units from the ED begin receiving the assigned crystalloid during evaluation and management in the ED (NCT02614040). Clinical outcomes of patients treated with study crystalloids in the ED and hospitalized outside the ICU will be recorded and reported separately. Similarly, to the extent that is logistically feasible, for patients identified in the operating room as coming from or being admitted to one of the participating ICUs, the request is made that they receive the fluid assigned to the corresponding ICU during their operative

procedure. Fluid administered prior to enrollment by the emergency medical system and outside hospitals, and fluid administered after discharge from the ICU, is not controlled by the study.

Each day patients receive the crystalloid to which their ICU is currently assigned. The necessity that an intravenous crystalloid be clinically available at all times precluded the use of washout periods and patients who remain in the ICU through a crossover (i.e., from one calendar month to another) may potentially be exposed to both types of crystalloid. Although this introduces the potential for contamination of study groups, in a pilot trial at the same institution, the total volume of non-assigned crystalloid administered due to the lack of a washout period was less than 125 mL per patient[14]. As described in the *Statistical Analysis* section below, patients will be analyzed in the group to which they were assigned at the time of study enrollment in an intention-to-treat fashion (e.g., a patient admitted to an ICU during a month assigned to saline will be analyzed in the saline group even if that patient remains in the ICU after the ICU switches assignment to balanced crystalloids).

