**Table E3. Intravenous fluids and blood products.**

	Saline	Balanced Crystalloid	
	(n = )	(n = )	P value
0.9% sodium chloride, median [IQR]; mean ± SD, mL			
Prior to enrollment on Day 0	--	--	--
Cumulative volume from enrollment through day 3	--	--	--
Cumulative volume from enrollment through day 7	--	--	--
Cumulative volume from enrollment through day 14	--	--	--
Cumulative volume from enrollment through day 30	--	--	--
Cumulative volume from enrollment through ICU transfer	--	--	--
Prior to an ICU crossover in fluid assignment	--	--	--
After an ICU crossover in fluid assignment	--	--	--
Cumulative volume from ICU transfer to hospital discharge	--	--	--
Lactated Ringer's, median [IQR]; mean ± SD, mL			
Prior to enrollment on Day 0	--	--	--
Cumulative volume from enrollment through day 3	--	--	--
Cumulative volume from enrollment through day 7	--	--	--
Cumulative volume from enrollment through day 14	--	--	--
Cumulative volume from enrollment through day 30	--	--	--
Cumulative volume from enrollment through ICU transfer	--	--	--
Cumulative volume from ICU transfer to hospital discharge	--	--	--
Plasma-Lyte A®, median [IQR]; mean ± SD, mL			
Prior to enrollment on Day 0	--	--	--
Cumulative volume from enrollment through day 3	--	--	--
Cumulative volume from enrollment through day 7	--	--	--
Cumulative volume from enrollment through day 14	--	--	--
Cumulative volume from enrollment through day 30	--	--	--
Cumulative volume from enrollment through ICU transfer	--	--	--
Cumulative volume from ICU transfer to hospital discharge	--	--	--
Balanced crystalloid, median [IQR]; mean ± SD, mL			
Prior to enrollment on Day 0	--	--	--
Cumulative volume from enrollment through day 3	--	--	--
Cumulative volume from enrollment through day 7	--	--	--
Cumulative volume from enrollment through day 14	--	--	--
Cumulative volume from enrollment through day 30	--	--	--
Cumulative volume from enrollment through ICU transfer	--	--	--
Prior to an ICU crossover in fluid assignment	--	--	--
After an ICU crossover in fluid assignment	--	--	--
Cumulative volume from ICU transfer to hospital discharge	--	--	--
"Hypotonic" crystalloid, median [IQR]; mean ± SD, mL			
Prior to enrollment on Day 0	--	--	--
Cumulative volume from enrollment through day 3	--	--	--
Cumulative volume from enrollment through day 7	--	--	--

Cumulative volume from enrollment through day 14	--	--	--
Cumulative volume from enrollment through day 30	--	--	--

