## Appendix 2: Definitions of Study Variables

### **Fluids**

**Intravenous fluid** – For the SMART study, intravenous fluid will be defined as the intravenous administration of any formulation of any volume at any rate of 0.9% sodium chloride, Lactated Ringer's, Plasma-Lyte A®; 0.45% sodium chloride, 0.225% sodium chloride, dextrose in water, 20% or 5% human albumin solution, gelatins, dextrans, or hydroxyethyl starches. This will include fluid given as a bolus, fluid given as maintenance infusions, fluid given as flushes, fluid given as 'piggy-back' infusions for IV medications, fluid given through pressure-bag systems, fluid given as a part of thermodilution of pulmonary artery catheters, and fluid given to maintain the patency of peripheral venous access. This will not include carrier fluid for medications and oral fluids.

**Isotonic crystalloid** – For the SMART study, the term isotonic crystalloid will be used to refer to any of 0.9% sodium chloride, Lactated Ringer's, or Plasma-Lyte A®. Use of the term isotonic crystalloid is intended to distinguish these three fluids from colloid solutions and from significantly hypotonic (0.45% sodium chloride) or hypertonic (3% sodium chloride) crystalloid solutions, rather than to imply that the tonicities of 0.9% sodium chloride, Lactated Ringer's, or Plasma-Lyte A® are precisely comparable to extracellular fluid.

**Saline** – Saline will refer to 0.9% sodium chloride.

**Balanced Crystalloid** – For the SMART study, Lactated Ringer's or Plasma-Lyte A® will be referred to as balanced crystalloids.

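### The 30-day volume in the main secondary analysis mixes assigned fluid with uncontrolled post-ICU fluid and opposite-type post-crossover fluid, so it does not measure dose of the assigned crystalloid

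*Combined protocol and SAP*

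**What the plan says.** The SAP (Main Secondary Analysis) models MAKE30 by logistic regression with "independent variables of study group, total isotonic crystalloid received between enrollment and 30 days, and the interaction between the two". Section 12.0 of the 6/15/17 protocol and the published protocol paper repeat this. The stated purpose is to learn whether there is any volume at which balanced crystalloid lowers the risk of MAKE30, and the SAP Discussion describes the aim as a dose-response relationship.

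Four other statements fix what that volume contains.

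- SAP Appendix 2 (Fluids): "the term isotonic crystalloid will be used to refer to any of 0.9% sodium chloride", lactated Ringer's or Plasma-Lyte A. Neither location nor assignment enters the definition.
- Protocol section 8.2: patients are treated with the ICU's assigned fluid "until they are physically discharged from the ICU".
- SAP, Study Interventions, on later fluid: "fluid administered after discharge from the ICU, is not controlled by the study".
- Same section, on crossovers: "Each day patients receive the crystalloid to which their ICU is currently assigned", so those who stay across a month boundary "may potentially be exposed to both types of crystalloid". They are still analyzed in the group assigned at enrollment. In the pilot, "the total volume of non-assigned crystalloid administered due to the lack of a washout period was less than 125 mL per patient".

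The SAP recognizes that volume arises after enrollment. It plans three sensitivity analyses: volume in the first 72 hours, volume predicted from enrollment characteristics, and a population with at least 500 mL in 72 hours. None limits actual volume to the ICU stay or to the assigned period. The washout and per-protocol exclusions repeat only the primary analysis. Table E3 does tabulate the pieces separately, with a row for "Cumulative volume from ICU transfer to hospital discharge" and rows for volume before and after an ICU crossover.

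**The concern.** A dose-response question needs a variable that measures dose of the fluid being compared. Take two invented patients in the saline group. One receives 2 L of saline in the ICU and 6 L of lactated Ringer's on the ward; the other receives 8 L of saline in the ICU. Both enter the model as 8 L, saline. Ward litres carry no assigned contrast, and post-crossover litres carry the reverse of the patient's group label.

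The post-ICU part also depends on the outcome. A patient who dies in the ICU receives no ward fluid, and death is a component of MAKE30.

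At stake is the reading of the plan's leading secondary result. The volume at which the fitted curves cross could be quoted as the exposure at which fluid choice starts to matter, and the slope as evidence for or against a dose-response. The primary analysis does not use volume and is untouched.

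**Working it through.** **1. The plan's own figure.** The only stated power is for the primary comparison: 14,000 patients, MAKE30 about 15%, absolute difference 1.9%, two-sided alpha 0.05. With 7,000 per arm and 15.0% versus 13.1%, power is 89.9%, so the stated 90% reproduces. If 15% is read as the two-arm average (15.95% versus 14.05%), power is 88.3%. Neither figure bears on this point: the plan gives no power, effect size or threshold for the volume interaction.

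**2. What the fitted model estimates.** Let A be assigned-period volume, U the remaining volume and T = A + U. If the log odds ratio is b1 + b3·A, the crossing volume is V_A = −b1/b3. Fitting with T instead, and taking U unrelated to the event given A, to first order:

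- the interaction is multiplied by λ = [var(A) + cov(A,U)] / [var(A) + 2cov(A,U) + var(U)];
- the crossing point moves by mean(U) + (V_A − mean(A))·(1/λ − 1).

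So λ is below 1 when U is independent of A or positively related to it, and above 1 when cov(A,U) + var(U) is negative. The crossing point usually rises because mean(U) is positive. If U is exactly proportional to A, the change is one of units. With 1 L on a 3 L mean, the coefficient is multiplied by 3/4, a 3 L crossing point becomes 4 L, and the z statistic does not change.

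**3. Size under stated assumptions.** None of these inputs is in the documents: A lognormal with mean about 3 L, interaction −0.05 on the log-odds scale per litre, true crossing point 0.5 to 5 L, mean U as listed, 1.5 million simulated patients per scenario.

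| Extra volume U | Interaction, T model / A model | Rise in crossing point |
|---|---|---|
| Crossover only, mean 0.125 L | 0.94–0.97 | 0 to 0.24 L |
| Post-ICU, independent of A, 0.5 L | about 0.99 | about 0.5 L |
| Same, 1 L | about 0.96 | 0.9 to 1.1 L |
| Same, 2 L | 0.79–0.83 | 1.5 to 2.4 L |
| Post-ICU, positively related or proportional to A, 1 L | 0.70–0.75 | 0.2 to 1.8 L |
| Post-ICU, negatively related to A, 0.5–2 L | 1.03–1.08 | 0.4 to 2.0 L |
| Post-ICU, lower or absent in patients with the event, 0.5–2 L | 1.12–1.96 | 0.2 to 1.7 L |

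Check against step 2 for the independent 2 L case with a true crossing point of 3 L (mean A 2.96, fitted V_A 3.10, λ 0.742): 2.0 + 0.14 × (1/0.742 − 1) = 2.05 L. The simulation gave 5.05 − 3.10 = 1.95 L. A separate set of runs with post-ICU fluid and a true crossing point of 2 L gave rises of about 0.25 to 1.6 L.

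**4. The crossover part alone.** The pilot ceiling of 0.125 L is 0.125/3 = 4.2% of an assumed 3 L mean, or 0.125/4 = 3.1% of 4 L, the volume that the SAP Discussion expects at least a quarter of patients to exceed. The interaction changes by about 3 to 6%. The pilot figure covers only the lack of washout. Patients transferred between study ICUs also receive the current unit's fluid (protocol section 7.5), and no volume is given for them.

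**5. Does the 72-hour version remove the problem?** The SAP says fewer than 10% of patients stay beyond 7 days. Taking exactly 10% and assuming exponential stays, mean stay is 7/ln(10) = 3.04 days. The share leaving the ICU within 72 hours is 1 − 0.1^(3/7) = 63%, and about 3.04/30.4 = 10% would meet a crossover. The shorter window drops late fluid but can still count ward fluid for most patients.

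**The case against.** The strongest reply is that the SAP chose overall volume deliberately, as a pragmatic measure, and already flags it as post-enrollment. The predicted-volume analysis keeps a trial patient's own ward litres out of the variable. The SAP Discussion says most fluid is given in the emergency department and the first 12 ICU hours, which argues against a large ward share. Post-crossover fluid is under 125 mL per patient.

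Much of this stands. Crossover fluid is a minor contributor on average. The early concentration of fluid makes the upper scenarios less likely, although emergency department fluid precedes enrollment, so the denominators differ. The predicted-volume model protects against the patient's later course, but it still substitutes a prediction of total receipt. It does not estimate the effect by actual dose of assigned fluid.

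Three stronger readings are tempting and unsupported.

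- A reader might infer that the trial leaves post-crossover fluid unassigned. It assigns that fluid; the mismatch is with the patient's analysis group.
- A reader might infer that the interaction is diluted and power lost. Direction depends on how ward volume relates to ICU volume and to the event. With ward fluid lower or absent in event patients, the simulations above gave inflation; under other assumptions, removing ward fluid for 25 to 50% of events still gave dilution.
- A reader might assume a ward share of 10 to 40% and multiply the crossing volume by 1/(1 − share), that is 1.11 to 1.67. The share is not in the documents. The multiplier is exact only under proportionality, where z does not change.

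A cut at the next crossover also has a cost: a long-stay patient admitted on the last day of a month would be recorded as low volume. That objection stands and shapes the fix.

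**Conclusion.** The point holds as a mismatch between the volume variable and the dose-response question. The 30-day total mixes assigned-period crystalloid with post-ICU crystalloid that the trial does not control and post-crossover crystalloid opposite to the analysis group. No planned analysis isolates the first part by actual volume. The crossing volume tends to be overstated, and the interaction cannot be read as dose of assigned fluid.

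In the post-ICU scenarios the crossing point rose by about 0.2 to 2.4 L, while the interaction ranged from 0.70 to 1.96 times its assigned-period value. These ranges rest on assumed volumes and relationships, so they show what is possible and do not estimate the bias in this trial. Only the crossover part has a documented size, and it is small. The upward shift is a tendency: by the formula in step 2 it can approach zero when the true crossing point lies well below mean volume. This is an inexpensive improvement to a secondary analysis.

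**What to change.** Fit the same group-by-volume logistic model with isotonic crystalloid received from enrollment until the earlier of (a) leaving the enrolling study ICU or (b) that ICU's next change of assignment. Report it beside the total 30-day model. Apply the same cut to the 72-hour version, and keep the predicted-volume analysis, because assigned-period volume is still a post-enrollment variable. Since the crossover cut makes volume depend partly on admission date, also show a version cut only at ICU transfer.

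The cost is a paragraph of SAP text and one derived variable. Table E3 already plans the splits at ICU transfer and at crossover, and protocol section 8.4 collects time, volume and location for each fluid order and the times of ICU transfer. Under the SAP's own rule, an analysis added after the final plan would be labeled post hoc and hypothesis-generating.
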